## **8.2 Other Protocol-Required Drugs**

There are no other protocol-required drugs.

## **8.3 Other Protocol-Required Treatment Procedures**

There are no other protocol-required treatment procedures for this study.

## **8.4 Treatment Precautions**

There are no specific treatment precautions required for this study.

## **8.5 Safety Monitoring Rules**

In addition to the standard monitoring of clinical safety parameters, the following guidelines are provided for the monitoring of selected parameters chosen based on preclinical and clinical observations.

Please refer also to the 'Guidance for Investigator' section of the Investigator's Brochure.

For the purposes of safety monitoring baseline is defined as the average of Day 1 pre-dose assessment and the last measurement prior to Day 1.

**Confirmation Guidance:** At any time during the Study (Randomized Treatment, OLE, or Post-Treatment Periods), the initial clinical laboratory results meeting the safety monitoring criteria presented below **must be confirmed** by performing measurements (ideally in the same laboratory that performed the initial measurement) on new specimens. All new specimen collections should take place as soon as possible (ideally within 3 days of the initial collection). For stopping rules, if the initial laboratory result is observed during the Treatment Period, the results from the retest **must be available** prior to administering the next dose of Study Drug.

**Re-dosing Guidance:** Patients with initial laboratory test values that reach a stopping rule must not be re-dosed until the re-test results are available. In general, patients who do not meet the stopping rules based upon retest may continue dosing. However, the Investigator and the Sponsor Medical Monitor (or appropriately qualified designee) should confer as to whether additional close monitoring of the patient is appropriate. Reduction in dose or dose frequency may also be initiated as noted in [Section 8.7](#). If any of the stopping criteria described below are met below (refer to [Sections 8.6.1](#) to [8.6.3](#)) and are confirmed, the patient will be dose paused or permanently discontinued (as described in the appropriate stopping criterion) from further treatment with Study Drug, and evaluated fully as outlined below and in consultation with the Sponsor Medical Monitor or appropriately qualified designee, and will be entered into the post-treatment evaluation portion of the study (see [Section 8.8](#)).

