#### **6.2.2      *Laboratory Assessments***

Laboratory analyte samples will be collected throughout the study as indicated in [Appendix A](#). A list of these analytes is contained in [Appendix B](#).

Each time a hematology lab is drawn and sent to the central laboratory for analysis an additional sample should be collected in parallel and analyzed locally. In the event that both the central and local sample are unreportable or uninterpretable (e.g., due to hemolyzed or clumped blood samples) another sample must be repeated within 1 week and the result must be reviewed by the Investigator and confirmed to be acceptable before dosing can continue. All platelet count results will be promptly reviewed by the Investigator to determine if the count has met a stopping rule, or the dose reduction rule of  $100,000/\text{mm}^3$ , or the dose pause rule of  $75,000/\text{mm}^3$ .

Any case of a platelet count  $\leq 50,000/\text{mm}^3$  should be reported in an expedited fashion to the Sponsor.

[REDACTED]

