### **8.6.3 Stopping Rules for Platelet Count Results**

Actions to be taken in the event of a low platelet count are summarized in [Table 4](#) below.

In the event of a platelet count less than  $75,000/\text{mm}^3$  that is associated with major bleeding or clinically-relevant non-major bleeding (defined below; [Schulman et al. 2005](#)), dosing of a patient with Study Drug will be stopped permanently. The follow-up schedule for any events meeting this stopping criterion will be determined by the Investigator in consultation with the Sponsor Medical Monitor.

In the event of any platelet count less than  $50,000/\text{mm}^3$ , or a platelet count less than  $75,000/\text{mm}^3$  that occurs while the patient is on dosing at 300 mg every 2 weeks then dosing of a patient with volanesorsen will be stopped permanently. Platelet count will be monitored as outlined in [Table 4](#).

Administration of corticosteroids is recommended for patients whose platelet count is less than  $50,000/\text{mm}^3$ . Recovery in platelet count may be accelerated by administration of high dose corticosteroids. Treatment guidelines for immune thrombocytopenia ([Provan et al. 2010](#)) recommend dexamethasone 40 mg daily for 4 days every 2-4 wk for 1-4 cycles; prednisolone 0.5-2 mg/kg/day for 2-4 weeks then taper; or methylprednisolone 30 mg/kg/day for 7 days (**note:** may require continuation with oral corticosteroids after methylprednisolone).

Triglyceride levels will be monitored weekly, and AE monitoring will continue during corticosteroid treatment and the laboratory alert will be changed from an increase of 2,000 to 500 mg/dL during that period.

In the event of a platelet count less than  $75,000/\text{mm}^3$ , and in the absence of major bleeding or clinically-relevant non-major bleeding (defined below; [Schulman et al. 2005](#)), dosing of a patient with Study Drug will be suspended temporarily until the platelet count has recovered to  $\geq 100,000/\text{mm}^3$ . If dosing is reinitiated it should be at a reduced dose frequency of 300 mg every 2 weeks (refer to [Section 8.7](#)). The suitability of the patient for reinitiation of dosing will be determined by the Investigator in consultation with the Study Medical Monitor and will be based on factors such as the original rate of decline in the patient's platelet count, whether any bleeding events were experienced by the patient, and the speed of recovery of platelet count upon holding of dosing.

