**Table 4 Actions in Patients with Low Platelet Count or Drop in Platelet Count**  
*Continued*

Platelet Count on Rx	Drug Dose	Monitoring
100K/mm  - > 75K/mm 	Permanently reduce dose frequency to 300 mg every 2 weeks	
75K/mm  - > 50K/mm 	If occurs while on dose of 300 mg every 2 weeks then permanently discontinue Study Drug, otherwise dose pause When platelet count returns to > 100K/mm  restart dosing at dose frequency of 300 mg every 2 weeks only if approved by Sponsor Medical Monitor	Monitor every 2-3 days until 2 successive values are > 75K/mm  then monitor every 1 week Consider discontinuation of antiplatelet agents/NSAIDS/ anticoagulant medication
≤ 50K/mm 	
 
• Permanently discontinue Study Drug
 
	
 
• Monitor daily until 2 successive values show improvement then monitor every 2-3 days until 2 successive values are > 75K/mm^3 then monitor every 1 week
 
• Patient should be evaluated by a hematologist to provide diagnostic and therapeutic management
 
• Steroids recommended*. It is strongly recommended that, unless the patient has a medical contraindication to receiving glucocorticoids, the patient receives glucocorticoid therapy to reverse the platelet decline.
 
• Monitor triglyceride levels weekly and continue AE monitoring during steroid therapy
 
• Discontinue antiplatelet agents/NSAIDS/ anticoagulant medication while platelet count is < 50K/mm^3 if possible
 

\*\* Recovery in platelet count may be accelerated by administration of high dose corticosteroids. Treatment guidelines for immune thrombocytopenia ([Provan et al. 2010](#)) recommend dexamethasone 40 mg daily for 4 days every 2-4 wk for 1-4 cycles; prednisolone 0.5-2 mg/kg/day for 2-4 weeks then taper; or methylprednisolone 30 mg/kg/day for 7 days (**note:** may require continuation with oral corticosteroids after methylprednisolone)

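### Protocol 8.5 applies its retest-and-confirm step to the platelet stopping rules by name, but 8.6.3, Table 4 and 8.8 contain no confirmation step, so a low count that recovers on retest gets different dosing instructions

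*Protocol*

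**What the plan says.** **Protocol 8.5 (Confirmation and Re-dosing Guidance).** Initial results that meet the criteria must be confirmed on new specimens, ideally within 3 days and in the same laboratory. While that is pending, "Patients with initial laboratory test values that reach a stopping rule must not be re-dosed until the re-test results are available". Afterwards, "In general, patients who do not meet the stopping rules based upon retest may continue dosing", with the Investigator and Medical Monitor conferring on closer monitoring and with dose or frequency reduction under 8.7 as an option. When the criteria in 8.6.1 to 8.6.3 are met "and are confirmed, the patient will be dose paused or permanently discontinued". Section 8.6.3 is the platelet rule.

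**Protocol 8.6.3.** The permanent-stop sentence opens "In the event of any platelet count less than" 50,000/mm3. It also covers a count below 75,000 on every-2-week dosing. For a count below 75,000 without major or clinically relevant non-major bleeding, "dosing of a patient with Study Drug will be suspended temporarily until the platelet count has recovered to" at least 100,000, with any restart at the every-2-week frequency. No limb mentions a retest.

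**Table 4.** The lowest tier, and the 75K to above 50K tier for a patient already on every-2-week dosing, say to "permanently discontinue Study Drug". For a patient on weekly dosing the 75K to above 50K tier is a pause. The 100K to above 75K tier is a permanent reduction to every 2 weeks. The repeat counts in the monitoring column follow the action; they are not a condition for it.

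**Protocol 8.7 and 8.8.** Section 8.7 makes 8.6.3 and Table 4 mandatory for platelet dose adjustments. Section 8.8 requires permanent discontinuation when laboratory abnormalities meet a stopping rule in 8.6. Neither mentions confirmation.

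**Protocol 6.2.2.** With each central hematology sample, "an additional sample should be collected in parallel and analyzed locally", and all platelet results are reviewed against the stopping rules.

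**The concern.** The question is whether one platelet count is enough to trigger the action, or whether a second must agree. The neighbouring rules answer it for their own parameters: the liver rules in 8.6.1 require confirmed results and the renal rules in 8.6.2 require changes that persist over 2 consecutive weeks. The platelet rule has neither phrase, so its silence can be read as deliberate. Yet 8.5 lists that same rule among those that take effect once confirmed.

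Falls in platelet count are a serious known risk of this drug. Protocol 2.3.4 reports 6 patients with pronounced falls that led to interruption or stopping, 2 of them hospitalised with counts below 25,000. Two sites, each following the protocol, could handle identical counts differently: one resumes dosing after a reassuring retest, the other suspends or permanently ends treatment. Exposure and discontinuation would then depend partly on which section a site relied on.

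**Working it through.** The plan states no figure on this point, so the check is to set the rules side by side and apply each to the same counts.

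**Inputs.** Thresholds of 50,000, 75,000 and 100,000/mm3 from 8.6.3 and Table 4; confirmation and re-dosing text from 8.5. The count pairs are assumed for illustration. All cases assume no bleeding, and dosing is held between the two counts as 8.5 requires. Counts at an exact threshold are avoided, so differences in inequality signs play no part.

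**Reading A:** 8.5 governs, and an unmet retest means the stopping rule is not confirmed. Table 4 still applies to the retest value.

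**Reading B:** 8.6.3, Table 4 and 8.8 act on the first count.

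| Case | Initial, then retest | Reading A | Reading B |
|---|---|---|---|
| 1. Weekly dosing | 48,000, then 80,000 | Dosing allowed, at the frequency in the 100K to above 75K row | Permanent stop |
| 2. Weekly dosing | 70,000, then 82,000 | Dosing allowed, at the reduced frequency in that row | Suspended until at least 100,000 |
| 3. Every-2-week dosing | 70,000, then 85,000 | Dosing allowed | Permanent stop |
| 4. Weekly dosing | 48,000, then 60,000 | Below-50,000 rule unconfirmed, below-75,000 rule still met: pause | Permanent stop |
| 5. Weekly dosing | 48,000, then 45,000 | Permanent stop | Permanent stop |

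**Reasoning.**
1. In cases 1 to 3 the retest is above 75,000, so no stopping rule is met on retest and 8.5 permits dosing. Reading B does not.
2. Case 2 is the mildest of these. Recovery above 75,000 clears the retest, but 8.6.3 sets the bar for resuming at 100,000. The difference is reduced-frequency dosing now against a suspension that may later end at that same frequency.
3. In case 4 neither reading doses the patient, but a pause and a permanent stop are not the same.
4. In case 5 the retest confirms and the sections agree. Disagreement therefore needs a retest that rises back over a threshold.
5. The wording of 8.6.3 is not uniform. The word any attaches only to the below-50,000 limb. For the below-75,000 limbs, and for Table 4, the single-count reading rests on the absence of a confirmation step.

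**Paired counts.** Section 6.2.2 deals expressly with the case where both the central and the local sample cannot be interpreted. It does not say what follows when one crosses a threshold and the other does not.

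**The case against.** The best defence is that the texts can be read together. On that view 8.5 is a general procedure (hold, retest, act as the relevant criterion describes), 8.6.3 supplies thresholds and actions, and confirmation already covers platelets by name. That reading is available. But it turns any count below 50,000 into any confirmed count, and it bypasses the 100,000 recovery bar after an unconfirmed value below 75,000. Nothing in 8.6.3 says either.

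The opposite defence is that 8.7 settles it, being mandatory and platelet-specific where 8.5 speaks only in general terms. It is the natural tie-breaker, but it does not say confirmation is waived, and 8.5 itself cites both 8.6.3 and 8.7. Protocol 8.5.3 and Table 4 also require the study doctor or a designee to authorise each dose on an acceptable platelet value. That is a real safeguard, but it does not say whether the first count or the retest decides what is acceptable.

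On the paired counts, 6.2.2 has every result reviewed against the rules, which suggests that either count may suffice. It stops short of saying so, and this is a secondary matter.

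A reader might infer that the protocol orders the same patient to be both re-dosed and stopped. It does not: 8.5 bars dosing until the retest and afterwards only permits it. Nor is the contrast one of unrestricted weekly dosing against stopping, because retests of 80,000 or 82,000 fall in Table 4's reduced-frequency row.

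**Conclusion.** The inconsistency stands. Section 8.5 makes confirmation a condition of the platelet stopping rules, while 8.6.3, Table 4 and 8.8 state those rules without it, and no passage says which prevails. For a low count whose retest recovers over the threshold, the result is permitted dosing against permanent stop (cases 1 and 3), reduced-frequency dosing against suspension (case 2), or pause against permanent stop (case 4). The counts are assumed and serve only to show where the rules part.

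The size cannot be given as a number of patients. A reader might take the 6 of 182 dosed patients in Protocol 2.3.4 (6/182 = 3.3%) as an estimate. Those are pronounced falls that led to interruption or stopping, not low counts that failed to confirm, and the documents give no rate for the latter. They show that the risk is serious, not how often the sections will conflict.

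A reader might also infer that the SAP must change. It need not. SAP 3.7.4 already tabulates platelet categories on worst and on confirmed values, and its stopping-rule listing records patients who actually terminated treatment. The point does not touch the primary endpoint's definition or model.

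**What to change.** Reconcile Protocol 8.5, 8.6.3, Table 4, 8.7 and 8.8. For each platelet tier, state whether a single count or a confirmed count triggers the action. Then make the text match: either correct the cross-reference in 8.5 so that it no longer reaches 8.6.3, or add the confirmation step to 8.6.3 and Table 4, with 8.7 and 8.8 worded consistently. At the same time, say how paired central and local counts are handled when only one crosses a threshold. Which rule to adopt is a clinical decision for the sponsor and DSMB, and this review takes no position on it.

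The cost is a wording change in those sections and a memo to sites. No new procedure or SAP amendment is needed.

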### **8.5.1 Safety Monitoring for Liver Chemistry Tests**

The following rules are adapted from the draft guidance for industry, “Drug-Induced Liver Injury: Premarketing Clinical Evaluation,” issued by the U.S. Department of Health and Human Services, Food and Drug Administration, July 2009. For a definition of baseline please refer to guidance in [Section 8.5](#) above.

#### For patients with Baseline ALT or AST below 2 x ULN

In the event of an ALT or AST measurement that is  $> 3 \times$  ULN (or the greater of 2 x Baseline value or 3 x ULN if the Baseline value was  $>$  ULN) at any time during the Study (Randomized Treatment, OLE, or Post-Treatment Period), the initial measurement(s) should be confirmed as described above. Additional, confirmatory measurements should also be performed if ALT or AST levels increase to 5 x ULN.

#### For patients with Baseline ALT or AST between $> 2$ and $< 3 \times$ ULN

In the event of an ALT or AST measurement that is 2 x the Baseline level any time during the study (Randomized Treatment, OLE, or Post-Treatment Period), the initial measurement(s) should be confirmed as described above. Similarly, confirmatory measurements should also be performed if ALT or AST levels increase to 5 x ULN.

**Frequency of Repeat Measurements:** Patients with confirmed ALT or AST levels that are continuing to rise should have their liver chemistry tests (ALT, AST, ALP, international normalized ratio [INR] and total bilirubin) retested at least bi-monthly until levels stabilize and begin to recover (ALT and AST levels become  $\leq 1.2 \times$  ULN or 1.2 x Baseline value).

**Further Investigation into Liver Chemistry Elevations:** For patients with confirmed ALT or AST levels  $> 3 \times$  ULN (or the greater of 2 x Baseline value or 3 x ULN if the Baseline value was  $>$  ULN), the following evaluations should be performed:

1. Obtain a more detailed history of symptoms and prior and concurrent diseases
2. Obtain further history for concomitant drug use (including nonprescription medications, herbal and dietary supplement preparations), alcohol use, recreational drug use, and special diets
3. Obtain a history for exposure to environmental chemical agents and travel
4. Serology for viral hepatitis (hepatitis A virus [HAV] IgM, hepatitis B surface antigen [HBsAg], hepatitis C virus [HCV] antibody, CMV IgM, and EBV antibody panel)
5. Serology for autoimmune hepatitis (e.g., antinuclear antibody [ANA])

Additional liver evaluations, including gastroenterology/hepatology consultations, hepatic computed tomography (CT) or MRI scans, may be performed at the discretion of the Investigator, in consultation with the Sponsor Medical Monitor. Repetition of the above evaluations should be considered if a patient’s ALT and/or AST levels reach 5 x ULN.

### **8.5.2 Safety Monitoring for Renal Function**

Patients with confirmed persistent changes that are observed over 2 consecutive visits, at least 7 days apart, for the criterion below should be retested every 2 weeks with serum creatinine and urine chemistries until creatinine and P/C ratio stabilize:

- P/C ratio change from baseline  $> 50\%$  and  $\geq 1.5$  ULN

### **8.5.3 Safety Monitoring for Platelet Count Results**

Monitor every 1 week unless otherwise specified.

Study Drug administration is contingent on the availability of the immediately preceding test result. An interpretable platelet value must be available within 7 days prior to dosing. Only the study doctor or qualified designee can authorize continued Study Drug administration based on an acceptable platelet value. Patients should not administer a dose until they have been contacted by their study doctor or designee and told that it is acceptable to dose. Authorization to dose must be documented in the patient's medical records.

Due to the 1 to 2-year study duration it is anticipated that patients may undertake travel including vacations, which may impede weekly platelet monitoring. In some situations, it may be possible to arrange for local laboratory testing or use of the home healthcare service at their temporary location. The intent is to maintain weekly platelet monitoring and dosing where possible, as well as Investigator site contact with the study patients. However, if the above options are not possible, a temporary interruption of study treatment will be planned with a prompt blood draw upon the patient's return which must be reported and reviewed by the Investigator prior to the patient resuming dosing.

Actions to be taken in the event of reduced platelet count are shown in [Table 4](#) in Section 8.6.3.

The tests outlined in [Table 3](#) should also be performed as soon as possible. Additional lab tests will be determined by the Sponsor Medical Monitor or designee in consultation with the Investigator.

Any case of a platelet count  $\leq 50,000/\text{mm}^3$  should be reported in an expedited fashion to the Sponsor (See also Stopping Rules Section 8.6.3).

**Table 3      Labs to Be Performed in the Event of a Platelet Count Less than the Lower Limit of Normal (x2) or < 100,000/mm^3 (x1)\***

\*In patients who have any 2 occurrences (non-consecutive or consecutive) of platelet count less than the lower limit of normal or who have any 1 occurrence of platelets < 100,000/mm^3. Labs only need to be performed once. Labs may be collected over multiple visits, if blood requirements are a concern, as per Investigator discretion.

Note: The following labs may change as additional data is assessed, and sites will be updated regarding any changes.

To Be Performed at Local Lab
Peripheral smear (should be performed locally, fixed and sent to central lab for review)
Fibrinogen split products or D-dimer on fresh blood
To Be Performed at Central Lab
Citrated sample for platelets
Coagulation panel (PT/INR, aPTT)
CBC with reticulocytes
Folate (folic acid)
Vitamin B12
Fibrinogen
von Willebrand factor
Total globulins, total IgA, IgG and IgM
Complement: total C3, total C4, Bb, C5a
hsCRP
Helicobacter pylori (breath test)
Serology for:
HBV, HCV, HIV (if not done recently for screening)
Rubella
CMV
EBV
Parvo B19
Auto-antibody screen:
Antiphospholipid
Rheumatoid factor
Anti-dsDNA
Anti-thyroid
To Be Performed at Specialty Lab(s)
Antiplatelet antibodies and Anti-PF4 assay
Anti-ASO antibody

#### **8.5.4 Safety Monitoring for Minor Bleeding Events**

Minor bleeding events are those that do not fulfill the criteria for major bleeding or clinically-relevant, non-major bleeding events (which are defined in [Section 8.6.3](#)), for example excess bruising, petechiae, gingival bleeding on brushing teeth. If a minor bleeding event occurs, the Investigator must notify the Sponsor Medical Monitor and additional testing of coagulation parameters (activated partial thromboplastin time [aPTT], prothrombin time [PT], INR) and platelet count should be performed.

#### **8.5.5 Safety Monitoring for Constitutional Symptoms**

Patients will be instructed to promptly report any signs of symptoms of fever or constitutional symptoms that may arise during the study and the Investigator should closely evaluate all potential causes, including concomitant illness. Patients who experience persistent constitutional symptoms should be discussed with the Sponsor Medical Monitor or designee to determine whether additional monitoring or laboratory tests are required.

